**Study Information**

[figure not shown]
[figure not shown]
Indication	Understanding desensitization and cross-desensitization during allergen SL immunotherapy.
Phase:	Pre-clinical
Number of Subjects:	30

**Background and Rationale**

- Provide background on unanswered question(s) the study is attempting to answer (do not exceed one page)

During immediate hypersensitivity reactions (a.k.a. allergic reactions), cross-linking of IgE-bound Fc $\epsilon$ RI by antigens, including pollen proteins, food proteins, or self-proteins haptenized by medications, leads to rapid secretion of preformed and newly-synthesized mediators by mast cells and basophils. Depending on where mast cells are activated, these mediators can result in hives, angioedema, vomiting, diarrhea, bronchoconstriction, hypotension, and even death. Two principal immunologic phenomena have been exploited to prevent allergic reactions, from rhinitis to systemic anaphylaxis, in sensitive individuals: tolerance, a state of allergen-specific clinical unresponsiveness produced after years of treatment that lasts well beyond the duration of treatment; and desensitization, clinical unresponsiveness produced after hours of treatment that wanes soon after therapy is discontinued. Allergen-specific immunotherapy has been used to reduce the risk, severity, and duration of symptoms after exposure to inhaled allergens and insect stings by inducing long-term tolerance. Procedures to induce clinical desensitization have been employed for nearly 70 years for medications and for more than a century for foods.

Despite these empirical procedures being at the core of the clinical practice of Allergy & Immunology for many years, the mechanisms by which clinical unresponsiveness occur remain largely unknown. Experimental desensitization *in vitro* was demonstrated as early as 1995 to occur in guinea pig peritoneal mast cells and in primary human mast cells by 1998. In the latter study, first activating basophils or mast cells in calcium free buffer was necessary to achieve good desensitization, a practice not required for human desensitization. Also, desensitization appeared to result from the loss of antigen-specific IgE on the cell surface, because the ability of the mast cells to respond to antigen could be restored after incubating the desensitized cells with fresh antigen-specific IgE. Using a sequential-dose *in vitro* desensitization protocol, it was recently proposed that desensitization impairs the internalization of IgE/Fc $\epsilon$ RI complexes in cultured mouse bone marrow-derived mast cells. More recently, our group has utilized two different approaches to study the mechanisms of antigen-mediated desensitization. The first is an *in vitro* sequential desensitization model in which cultured primary human mast cells are initially sensitized with antigen-specific IgE and then desensitized by the addition of increasing concentrations of allergen, from 1 pg/ml to 10 ng/ml added every 15 minutes. The second is an *in vivo/ex vivo* model in which human volunteers, penicillin allergic by history and sensitive by skin testing, undergo an oral desensitization protocol consisting of ingestion of increasing doses of penicillin VK from 100 to 640,000 units every 15 minutes. Titration skin testing and blood collection for *ex vivo* analysis of basophil function was performed before and after desensitization.

Sublingual administration of medications first became established with development of sublingual nitroglycerin tablets for angina. In addition to the administration of small synthetic drugs, the mucosal surface also has been explored for vaccination strategies and introduction of small therapeutic proteins, such as insulin. For proteins, the sublingual route has the advantages of avoiding denaturation by the acidic gastric environment, degradation in the small intestine by pancreatic proteases, and hepatic metabolism when absorbed into the mesenteric circulation. Further, the placement of the protein(s) in tablets ensures prolonged contact with the sublingual mucosa, thereby enhancing absorption. Thus, tablet immunotherapy permits the gradual introduction of allergens or allergen-derived peptides either into the immune pathway through uptake by mucosal dendritic cells that then migrate to secondary gut-associated lymphoid tissue or into the vascular system to be distributed systemically. The former pathway is likely to be responsible for enhancing the production of Treg cells that could cause long-term antigen-specific tolerance, while the latter is likely to desensitize mast cells and/or basophils.

Cross-desensitization has been described in several biological receptor symptoms, though reports of this phenomenon in the context of Fc $\epsilon$ RI activation are few. In one report, cross-desensitization occurred in vitro with mast cells sensitized with both IgG and IgE. However, it has not been studied rigorously in a clinical setting, and thus the incidence of cross-desensitization among patients undergoing clinical desensitization or sublingual immunotherapy is unknown. As little is known about cross-desensitization, it is difficult to predict how this might affect the clinical practice of allergy. It is conceivable that the effect could be exploited to produce clinical benefit—if cross-desensitization could be attained during sublingual immunotherapy to a relatively innocuous allergen, perhaps it could be utilized to minimize the risks associated with other forms of allergen-specific immunotherapy, such as oral immunotherapy to foods.

## Objectives

- List the objectives to correspond directly with the listed hypotheses:

To induce clinical tolerance, a failure to respond to an allergen to which one was previously responsive, is an important objective for physicians, one that plays a significant role in the primary prevention of allergic reactions in the clinical practice of Allergy & Immunology. The tolerance resulting after standard subcutaneous immunotherapy to aeroallergen and insect venom allergens is long lasting and allergen-specific, and may involve antigen-specific T regulatory cells. In contrast, tolerance resulting from drug desensitization protocols is short-lived, and postulated to target mast cells and basophils. Research into the cellular and biochemical processes by which desensitization occurs has revealed that mast cells desensitized to one antigen in vitro, under certain conditions, lose the ability to degranulate to unrelated antigens or to direct Fc $\epsilon$ RI cross-linking. Preliminary data suggests that this cross-desensitization can happen in patients undergoing incremental desensitization, as described above, depending in part on the percentage of IgE targeted to the allergen used for desensitization. This proposal therefore aims to explore desensitization and cross-desensitization in human volunteers undergoing standard oral immunotherapy to grass or ragweed pollen.

**OBJECTIVE I:** Desensitization of cutaneous mast cells and blood basophils occurs during grass or ragweed pollen sublingual immunotherapy.

**OBJECTIVE II:** Cross-desensitization to unrelated allergens also occurs during grass or ragweed sublingual immunotherapy, depending in part on the portion of IgE targeting the allergen used for immunotherapy.

## Hypothesis

- List the clinical Hypotheses in order of priority:

**Objective I.** We expect to see desensitization of mast cells and basophils to the allergen utilized during SL immunotherapy, but not to G protein receptor-coupled ligands, such as codeine and C5a. Moreover, it will be of interest to explore whether the magnitude of allergen-specific IgE levels in plasma affects the occurrence,

magnitude, or timing of desensitization. For example, it is possible that allergen-specific IgE in the serum serves to block or delay the arrival of allergen at the surface of mast cells, but perhaps not at the surface of circulating basophils. On the other hand, formation of low levels of small IgE:allergen immune complexes in the circulation might facilitate desensitization. Furthermore, whether desensitization reduces the level of free allergen-specific IgE, and such reduced levels of allergen-specific IgE correlates with desensitization, will be of additional interest.

**Objective II:** Based on our in vitro studies, showing allergen cross-desensitization of mast cell in culture, we expect cross-desensitization of mast cells to occur during SL allergen immunotherapy in most subjects, perhaps depending on the relative amount of the IgE against the desensitizing allergen. A similar incidence of cross-desensitization in basophils is expected based on their similar, but not identical, biology compared to mast cells. Learning how to safely cross desensitize may have important clinical utility, e.g., giving clinicians the ability to desensitize with ragweed SL tablets, and then safely begin immunotherapy with a more dangerous allergen, e.g., peanut or insect venom, or to administer a needed drug, e.g., penicillin or ciprofloxacin, to which the patient had been previously sensitized.

### Study Design/Clinical Plan

- Provide a concise overview stating the type of experimental design

Central to both objectives of this proposal is the use of an approved sublingual immunotherapy protocol for allergen-specific immunotherapy. While our group has previously used increasing doses of swallowed penicillin in penicillin-sensitive patients to produce a state of clinical desensitization, the relatively low incidence of true penicillin allergy may make enrolling additional patients problematic. However, pollen allergic individuals are prevalent, and thus desensitization to such allergens is very feasible. Indeed, allergen-specific immunotherapy is considered standard of care for the treatment of allergic rhinoconjunctivitis. However, standard subcutaneous immunotherapy, administered by a weekly build-up followed by monthly maintenance injections is probably not ideal for desensitization. On the other hand, daily sublingual immunotherapy, as approved for patients with grass and ragweed allergic rhinoconjunctivitis, because of a relatively constant exposure, is more likely to result in desensitization.

**Inclusion criteria:** Adult subjects (18 to 65 years old, males and non-pregnant females) with a history of seasonal allergic rhinitis will be recruited for screening, which will include standard prick skin tests to: Timothy, Johnson, and Bermuda grass pollens; Oak, Ash, Hickory, and Mountain Cedar pollens; Short Ragweed pollen; *Dermatophagoides pteronyssinus* and *farinae*; and Cat and Dog allergenic extracts. The grass and tree pollens were chosen to minimize genus cross-reactivity, as described in:

<https://ainotes.wikispaces.com/file/view/Allergen+Cross+Reactivity+Table.pdf>. Those who are sensitive to either Timothy or Short Ragweed pollen, and at least one but preferably two other allergens will be invited to participate.

**Exclusion criteria:** Subjects will be excluded for any one of the following: dermatographism or severe dermatologic condition, such as advanced eczema or psoriasis, that will not allow an adequate uninvolving area for skin testing; negative skin tests to Short Ragweed and Timothy or to at least one of the other listed aeroallergens tested; pregnancy; H1 receptor antihistamines taken within 7 days of testing; systemic steroids; omalizumab taken at any time; receiving or received immunotherapy; desensitized to any drug within 6 months; current uncontrolled or severe asthma; eosinophilic esophagitis; significant pulmonary, cardiovascular, renal, hepatobiliary, or neurological diseases, or another disease process felt to put subject at increased risk for an adverse event; hypersensitivity to any of the inactive ingredients in the tablet (fish gelatin and mannitol); mental illness or history of drug or alcohol abuse that, in the opinion of the investigator, would interfere with ability to comply with study requirements; or inability or unwillingness to give written informed consent.

**Protocol:** Subjects will undergo SL immunotherapy with either Timothy or Short Ragweed tablets (provided by Merck), taking one tablet per day, or will take a placebo tablet (provided by Merck). Titration skin testing to Timothy or Short Ragweed, to one or preferably two additional allergens to which the subject is sensitive, and

to codeine as a control for mast cell activation capability through a non-IgE-dependent pathway will be performed to determine the PC3 value (see below). Skin testing, including histamine and diluent controls, will be performed prior to and at one and four weeks after initiation of immunotherapy. At each time point, blood will be obtained to measure total and antigen-specific IgE levels, tryptase and cytokine levels, and basophil activation with the relevant allergens and C5a as a non-IgE-mediated control for basophil activation.

**First visit:** Patients will be considered for this study if they report multiple ( $\geq 2$ ) aeroallergen sensitivities, suggested by clinical history or previous skin or serum testing. Allergic sensitivities will be verified on the first visit by skin prick testing in the Clinical Research Services (CRS) unit in the North Hospital at Virginia Commonwealth University. Confirmation of Short ragweed or Timothy grass sensitivity and at least one, but preferably two, other unrelated aeroallergen sensitivities among the above list will be required for participation. Though there is conflicting evidence as to the correlation between wheal diameter from skin testing and the level of allergen-specific IgE measured in the serum, the allergen(s) with the largest wheal size will be selected for both the desensitizing allergen as well as for the allergens to test cross-desensitization.

Thirty subjects who qualify will then have blood drawn and undergo titration skin testing (see below) to the desensitizing allergen, to two other aeroallergens, and to codeine, from which PC3 values will be calculated. Wheal areas to histamine and diluent also will be determined. SL tablet immunotherapy will then begin with allergen tablets (n=15), as approved by the FDA, or placebo tablets (n=15) in a double-blind randomized manner.

**Second visit:** Patients will return to the CRS unit two weeks after SL immunotherapy has begun. At that time, titration skin testing will be performed to the same allergens plus codeine as on the First visit, along with a positive histamine and negative diluent control. Blood will also be collected for use in ex vivo analyses (see below).

**Third visit:** Patients will return to the CRS unit two months after SL immunotherapy has begun. At that time, titration skin testing will be performed to the same allergens plus codeine as on the First and Second visits, along with a positive histamine and negative diluent control. Blood will again be collected for use in ex vivo analyses (see below).

#### Subject Payments for Participation:

**Visit 1:** If potential subject fails screening, then no payment will be made. The individual will learn about their sensitivity to major aeroallergens. Upon completion of Visit 1, a \$50 payment will be made.

**Visit 2:** Upon completion of Visit 2, a \$50 payment will be made.

**Visit 3:** Upon completion of Visit 3, a \$200 payment will be made.

#### Treatment

- List the clinical dosage/dosage form, route, and dose regimen:

The Timothy grass pollen allergen tablet (2800 Bioequivalent Allergy Units/tablet) (GRASTEK, Merck), and the Short Ragweed pollen allergen tablet (12 Amb a 1-Units/tablet) (RAGWITEK, Merck) have shown clinical efficacy. The current proposal will use either the Timothy grass tablet or the Short Ragweed tablet, along with a placebo tablet, supplied by Merck. The allergen tablet used will depend on which allergen the subject is sensitive to, which one corresponds to the strongest titration skin test response, and which one corresponds to an out of season allergen at the time enrollment is planned.

Subjects will be randomized to receive either allergen tablets (n=15) or placebo tablets (n=15) in a double-blind manner. The tablet will be placed under the tongue, where it should remain until fully dissolved, after which the patient should avoid ingesting food or beverages for five minutes. This first dose will be administered in the CRS unit, where the subject will be observed for 30 min, being monitored for any sign of an allergic reaction. If there is no clinically significant reaction, the subject will continue taking one tablet per day at home. Mild itching inside the mouth is expected to occur in a substantial number of subjects. This reaction should

generally subside within an hour, should generally cease after about one week, and is not considered to be clinically significant. If a clinically significant reaction does occur, such as systemic anaphylaxis or an asthma exacerbation, the subject will be withdrawn from the study.

Oxygen, epinephrine (IM), diphenhydramine (PO and IV), ranitidine (PO and IV), albuterol for nebulization, and a nebulizer will be available, if needed, in the CRS unit. A code cart will be available in the CRS unit, and a code button is present on each CRS bed. If a code is called, the dedicated code team of the hospital will respond (typically within 2-3 minutes) and transport the subject to an intensive care unit, as appropriate. Prior to the code team response, a code will be initiated by the personnel in place; both the CRS nurses and the Allergy/Immunology fellows are ACLS-certified.

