Secondary outcomes will be analyzed by comparing the percent IgE specific for Timothy grass or Short Ragweed, depending on the subject's initial sensitization, with the fold change in PC3 values after treatment for Timothy grass or Short Ragweed (Objective I) or unrelated aeroallergen (Objective II). Comparisons between continuous variables will be performed by calculating Pearson or Spearman coefficients or by regression modeling.

Subgroup analysis may be performed on any of the above measures if deemed necessary. For example, it may be determined that subjects treated with Timothy grass immunotherapy are more likely to display cross-desensitization than those treated with Short Ragweed immunotherapy.

All calculations will be performed using a statistical analyses software package such as SigmaPlot (Systat, San Jose, CA) or SPSS (IBM, Armonk, NY).

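### The 15:15 randomisation is not stated to be stratified by tablet allergen (Timothy or Short Ragweed) and the primary tests carry no product term, so chance imbalance in product mix is left uncontrolled when it could be removed at almost no cost.

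*Combined protocol and SAP*

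**What the plan says.** Randomisation is described twice, under Treatment and under First visit in Study Design/Clinical Plan. The first reads "Subjects will be randomized to receive either allergen tablets (n=15) or placebo tablets (n=15) in a double-blind manner" and the second "allergen tablets (n=15), as approved by the FDA, or placebo tablets (n=15) in a double-blind randomized manner". Neither names a stratification factor, a block size or a list per product, and no other section does.

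The product is assigned by rule, not by chance. Treatment states: "The allergen tablet used will depend on which allergen the subject is sensitive to, which one corresponds to the strongest titration skin test response". It adds a season criterion: "which one corresponds to an out of season allergen at the time enrollment is planned". First visit says that "the allergen(s) with the largest wheal size will be selected for both the desensitizing allergen as well as for the allergens to test cross-desensitization", and has the baseline titration to the desensitizing allergen done before the first tablet. Every subject, placebo subjects included, therefore has an index allergen that is known at baseline.

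Statistical Plans defines the Objective I primary outcome as change in PC3 to whichever of the two allergens applies. It compares active with placebo by t test, repeated measures ANOVA, Mann-Whitney or Friedman, and lists no term for product. Objective II uses the same methods. Subgroup analysis is left to discretion, with this example: "it may be determined that subjects treated with Timothy grass immunotherapy are more likely to display cross-desensitization" than those treated with Short Ragweed. Timelines and Study Plans requests 900 active tablets and says that the division between the two products is not known.

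**The concern.** The index allergen is more than an ordinary covariate here. It fixes which extract is used to measure the primary endpoint, which product an active subject takes and, through the season rule, roughly when the subject is enrolled. The plan itself allows that the two products may behave differently.

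If the arms end up with different product mixes, part of the observed arm difference may reflect the mix. With one trial of 30 subjects, the realised allocation is the only one available to interpret. Any look at Timothy against Short Ragweed also needs placebo subjects for each allergen, because otherwise a product effect cannot be separated from a season or extract effect. If one product is uncommon, its placebo group could be very thin.

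**Working it through.** **The plan's own figure.** 15 + 15 = 30 subjects, which agrees with the stated total. Fifteen per group exceeds the pilot rule of 12 per group cited in Statistical Plans. Nothing below depends on the power statement for the IgE-ratio slope.

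**Inputs.** From the documents: 30 subjects, 15 per arm, no stratification stated. Assumed, because the documents do not give it: K, the number of subjects whose index allergen is the less common product, from 3 to 15.

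**Chance of imbalance.** With one unstratified 15:15 allocation, the number X of the K subjects who fall in the active arm is hypergeometric:

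P(X = x) = C(K, x) · C(30 − K, 15 − x) / C(30, 15), with C(30, 15) = 155,117,520.

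For K = 15, P(X ≤ 5 or X ≥ 10) = 2 × (0.0581 + 0.0120 + 0.0013 + 0.0001) = 0.143. For K = 10, P(X ≤ 3 or X ≥ 7) = 2 × (0.0975 + 0.0225 + 0.0025 + 0.0001) = 0.245.

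| K | Split of the smaller product between arms | Probability of that or worse |
|---|---|---|
| 15 | 10 v 5 | 14.3% |
| 12 | 8 v 4 | 26.4% |
| 10 | 7 v 3 | 24.5% |
| 8 | 6 v 2 | 21.5% |
| 6 | 5 v 1 | 16.9% |

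**Placebo subjects left in the smaller product (K − X).**

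| K | None | Two or fewer |
|---|---|---|
| 3 | 11.2% | 88.8% |
| 4 | 5.0% | 70.1% |
| 5 | 2.1% | 50.0% |
| 6 | 0.8% | 32.6% |
| 8 | 0.1% | 10.7% |
| 10 | 0.01% | 2.5% |

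**Effect on the realised arm difference at 10 v 5 (K = 15).** Let D be the difference between products in mean log10 PC3 change.

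- Products differ only under active treatment. Compared with an even mix, the active mean moves by D × (10/15 − 1/2) = D/6.
- PC3 change differs by allergen equally in both arms. The arm difference moves by D × (10/15 − 5/15) = D/3.

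The documents give no value for D. For an assumed range of 0.3 to 1.0 log10:

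- D/6 = 0.05 to 0.17 log10, a 1.1- to 1.5-fold shift in PC3.
- D/3 = 0.10 to 0.33 log10, a 1.3- to 2.2-fold shift.

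The upper end, D = 1.0, is itself a 10-fold difference, equal to the plan's threshold for clinically significant desensitization, so it is a generous limit.

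**With stratification.** Permuted blocks within each product hold the active-minus-placebo count in that product to at most half the block size: 1 for blocks of 2, 2 for blocks of 4. With blocks of 2, K = 10 splits 5/5, and no product with two or more subjects can lack a placebo subject.

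**Size of the subgroup even then.** The smaller product has at most 15 subjects, so at most 7 or 8 per arm, below the plan's own 12 per group.

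**The case against.** A reader might infer that index allergen is confounded with arm, so that the primary test is biased. The documents do not support this. The arms are randomised, allergen is independent of arm by design, and the expected difference in mix is zero. Chance imbalance adds variability; it does not create a systematic error.

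A reader might also take the larger shift, D/3, as the expected size. That requires placebo subjects to drift differently according to the allergen tested. The only hint in the plan of a product difference concerns treated subjects, and only for cross-desensitization, which points to D/6 and to a change in how the two products are weighted in the average effect. The outcome is change from each subject's own baseline, and the out-of-season rule limits natural exposure, so a large difference in both arms is not the natural assumption.

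A third tempting reading is that the Timothy-versus-Ragweed comparison will lose its controls altogether. That is negligible unless one product has about five or fewer subjects. The comparison is also optional, offered as an example, and would be small under any allocation.

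Finally, the documents do not say how the list is made. They leave stratification unstated and do not rule it out. The probabilities above assume a single list with no blocking; blocking over time could balance product in part, because the choice of tablet depends on season.

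All of these points stand, and they limit the weight of the concern. They do not remove it: the factor is known at baseline, helps to define the endpoint, and is neither balanced nor adjusted for in the stated plan.

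**Conclusion.** The point holds as a modest and inexpensive improvement. As written, the plan neither balances nor adjusts for tablet allergen. Material imbalance in mix would then arise in about 14% to 26% of allocations for K from 6 to 15, using the splits tabulated above. The consequence is loss of precision and a realised comparison that is harder to interpret. The size of any shift depends on the unknown D, and D/6 is the better supported of the two cases.

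For the optional subgroup, the realistic risk is a thin placebo group of two or fewer: 11% if the smaller product has 8 subjects and 33% if it has 6. The conclusions rest on an unblocked 15:15 list and on assumed values of K and D, since the documents give neither.

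**What to change.** Record each subject's index allergen before allocation; First visit already selects and titrates it before tablets begin. Then randomise 1:1 in small permuted blocks (2 or 4) within two strata, Timothy and Short Ragweed. Carry the stratum into the primary analyses of both objectives, as a model term if a parametric method is used or through a stratified rank test otherwise. If stratification is already intended, one sentence stating it and the matching analysis term would be enough.

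The cost is a second randomisation list and one model term. Incomplete last blocks may give 14:16 in place of 15:15: two odd strata can each be out by 1, or with blocks of 4 one stratum can be out by 2, and either way the arms differ by at most 2 in 30. The total stays at 30. The change improves balance and precision. It does not make the Timothy-versus-Ragweed subgroup adequately sized, and any such analysis should be labelled exploratory.
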